5.5. Confidentiality, responsibility and compensation

Information collected in this study will be exchanged exclusively between Merck, S.A. de C.V. and the PPD and will be treated as confidential.

Subjects will sign a consent specifying that they will receive an economical compensation for their participation in the study. The Sponsor will pay (o compensate, if applicable) the resulting injuries or diseases caused by the subjects' participation in the study until their resolution according to the medical opinion. The Sponsor will not pay if this is due to the subject's negligence, irresponsible conduct or medical conditions no related to the study.

The Ministry of Health, the Ethics and Investigation Committee and the Investigation Committee will be the only authorized bodies for reviewing the study documents (including the participant subjects' identity data) and the documents considered confidential by the PPD

and Merck, S. A. de C. V.

Study participant subjects' personal data will be confidential and will be protected by the Federal Law on the Protection of Personal Data held by Private Parties, which is stated in our PRIVACY NOTICE and can be checked in our website www.cecype.com.

6. Samples Chemical Analysis

Levothyroxine (T4) serum concentrations will be determined by liquid chromatography coupled in a mass detector/mass according to the physicochemical properties and reported in the international scientific literature (LC MS/MS), which will be validated prior to the start of the study according to the applicable guidelines and the study working plan, as well as to the applicable analytical technique, in compliance with the applicable Analytical Unit and Quality Assurance procedures, and according to the NOM-177-SSA1-2013 and the Good Laboratory Practice. The analytical method details will be described in the validation protocol.

7. Sample Size Determination, Pharmacokinetic and Statistical Analysis

The pharmacokinetic and statistical analysis for the levothyroxine serum concentrations will be carried at the PPD as per its standard operating procedures and in compliance with the NOM-177-SSA1-2013.

7.1. Sample Size Determination

The sample size determination was based on the variability seen in the most recent study conducted by the study Sponsor EMR200125-001 (comparative study of the levothyroxine formulations for approval in Europe) where the intrasubject variability for AUC_{0-72h} was 23.7 % and the C_{max} was 17.7 %. Using the most variable parameter AUC_{0-72h} , a difference of 5 %, a power of 90 % and applying the accepted bioequivalence range of 80 % to 125 %.

By using the Chow & Wang equation, and substituting the aforementioned values, a sample size of 34 subjects was obtained. If a drop rate of 20 % is considered, the sample size should be of 44 subjects.

7.2. Pharmacokinetic Analysis

The pharmacokinetic analysis will be obtained by using a non-compartmental analysis with the use of the current versions of the Phoenix® WinNonlin® software.

The following parameters will be determined. They will be calculated with the uncorrected data of the baseline levels (raw values), as well as the corrected values by baseline levels (adjusted values). The mean of the pre-dose levothyroxine levels should be used for the baseline adjustment of the post-dose levels. Any negative values obtained from baseline correction should be designated as zero (0):

C_{max}: maximum serum concentration observed directly from the concentration-time curve.

C_{max(aj)}: maximum serum concentration in pre dose corrected data.

t_{max}: time when the maximum serum concentration was obtained.

AUC_{0-t}: area under the curve of the serum concentration as a function of time, from time 0 until the last sampling time by means of the trapezoidal rule.

AUC_{0-t (aj)}: area under the curve of the serum concentration as function of time, from time 0 until the last sampling, by means of the trapezoidal rule in pre dose corrected data.

$$AUC_{0-\infty (aj)} = AUC_{0-t (aj)} + C_{t (aj)} / K_{el}$$

K_{el}: elimination constant, calculated from the semi-logarithmic graphic of the serum concentration as function of time. It is estimated by means of a simple linear regression analysis from at least the last three serum concentrations different to zero.

t_{1/2}: time of the half-life or elimination half-life calculated as $\ln (2) / K_{el}$

7.3. Statistical Analysis

7.3.1. Descriptive Statistics

Adjusted concentrations will be tabulated by treatment and by time of all subjects, stating the drug or formulation, the arithmetic mean, standard deviation and variation coefficient.

A descriptive statistic will be presented by the adjusted serum concentrations, by treatment globally (arithmetic mean, minimum value, maximum value, standard deviation and coefficient of variation).

The descriptive statistic will be determined from the individual adjusted pharmacokinetic parameters, by treatment, stating the period, sequence, quotient of the reference test, as well as its logarithm for the pharmacokinetic parameters used to determine the bioequivalence (geometric means, arithmetic mean, median, minimum value, maximum value, standard deviation and variation coefficient). This will only apply for evaluable subjects.

An evaluable subject will be one who has completed both periods of the study and has at least 60% of their samples with measurable concentrations, who has not presented vomiting or diarrhea before 2 times the median of the t_{max} or 2 times the value of t_{max} and who has not presented any situation that could modify the result of the study due to uncontrolled variables.

A graphic of the adjusted serum concentration against individual and average time in the arithmetic and semi-logarithmic scale.

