Pharmacokinetics	Branch of pharmacology studying the process of a drug in the body. It is intended to elucidate the drug's effect from its dosing until it has been fully cleared from the body (Goodman & Gilman, 12 th Edition).
Pharmacology	Science studying the origin and physicochemical properties, dosage form, pharmacodynamics (biochemical and physiological effects, and mechanism of action), pharmacokinetics (absorption, distribution, biotransformation and excretion), as well as the therapeutic effect of the chemical substance interacting with living organisms. In the strict sense of the word, pharmacology is considered as the drugs study; and whether they are beneficial or toxic (Goodman & Gilman, 12 th Edition).
Drug	Any substance or mix of substances of natural or synthetic origin which have therapeutic, prophylactic or rehabilitation effect, and a dosage form identified as such by its pharmacological activity, and physicochemical and biological characteristics (NOM-073-SSA1-2005).

Abbreviations

A	Absorption
AE	Adverse Event
AUC	Area under the curve of serum concentration
AUC_{0-t}	Area under the curve of serum concentration from time 0 until the last sampling time
AUC_{0-t(a)}	Area under the curve of serum concentration from time 0 until the last sampling time in pre dose corrected data
BC	Blood chemistry
BMI	Body Mass Index
°C	Celsius degrees
CBC	Complete blood count
CI	Confidence Interval
C_{max (aj)}	Maximum serum concentration in pre dose corrected data
C_{max}	Maximum serum concentration
CNFGV	National Center of Pharmacovigilance
COFEPRIS	Federal Commission for the Protection against Sanitary Risks
CRF	Case Report Form
DBP	Diastolic Blood Pressure
dL	Deciliter
E	Elimination
EIC	Ethics and Investigation Committee
FDA	Food and Drug Administration
g	Gravity or grams (depending on the context)
h	Hour
HIV	Human immunodeficiency virus
IC	Investigation Committee
ICF	Informed Consent Form
IUPAC	International Union of Pure and Applied Chemistry
K_{el}	Elimination constant
kg	Kilogram

µg	Micrograms
m²	Square meter
mg	Milligrams
min	Minute
mL	Milliliter
mmHg	Millimeters of mercury
PLM	Dictionary of Pharmaceutical Specialties
PPD	(SOP - Standard Operating Procedure)
SAE	Serious Adverse Event
SBP	Systolic Blood Pressure
SC	Serum concentration
PPD	
TSH	Thyroid stimulating hormone
T₃	Triiodothyronine
T₄	Thyroxine
t	Time
t_½	Elimination half-time
t_{max}	Time to reach the maximum serum concentration
UA	Urinalysis

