As the goal is to prove the lack of significant differences in the pharmacokinetic parameters where each subject is his/her own control, the chosen experimental design is one of those suggested by the NOM-177-SSA1-2013, crossed, open label, two sequences and two periods of treatment (scheme A - B and B - A), and single dose. Section 8.4.8.1 of this Standard states that drugs with a long half-life, crossed or parallel designs should include a limited sampling for at least 72 hours. However, prior studies showed that sampling times longer than 48 hours do not allow to characterize differences between exogenous and endogenous levothyroxine concentrations with certainty. Therefore, bioequivalence studies for this drug should be truncated up to 48 hours (*Guidance to Establish the Interchangeability of Oral Solid Drugs Containing Levothyroxine Sodium, COFEPRIS, 2017*). According to the, a 48-h sampling time, which is compliant with the Mexican health authorities' requirement, is proposed. In addition, it allows to characterize at least the 80 % of the AUC, by having 26 total samples and a wash-out period of 35 days between the two study periods.

Besides the inclusion and exclusion criteria, confounding variables to be controlled are: fasting state (at least 10 hours before the drug intake); morning time for the administration; volume and type of liquid for the drug intake; timing, type and quantity of food; liquid intake prior to the breakfast; restricted physical activity for a minimum that does not alter the heart rate; orthostatic or seated position till reaching the stated time for t_{max} ; abstinence of caffeine or theophylline containing products; controlled access to restrooms until the t_{max} is reached. Additionally, concomitant drugs are not allowed, except for the medical prescription for to adverse events. The occasional use of acetaminophen (maximum of 1000 mg per day, for three days) is allowed. While complying with the permitted dose, the use of paracetamol will not be reason for exclusion of the subject, nor for the study or pharmacokinetic analysis.

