4.5.5. Variable Assessment Periods

For the study conduct the following periods have been planned:

- **Screening:** within the 30 days prior to the dosing.
- **First period of the study:** from the 16.00 hours prior to the first dose and at least 48.00 hours post-dose.
- **Wash-out period:** 35 days between each dose.
- **Second period of the study:** from the 16.00 hours prior to the second dose and at least 48.00 hours post-dose.
- **Study withdrawal:** following the 48.00-hour sampling in the second period.

- ✚ **Follow-up of adverse events:** adverse events occurring in a 14-day period following the dosing in the second period will be reported. Adverse events that were presented during the follow-up period and continued unresolved in the final visit, should be followed until resolved are no longer considered as clinically relevant or can be explained.
- ✚ **Final Visit:** 14 days after last administration of the study product.
- ✚ **End of study:** The study will end when the last subject has been subjected to the activities described in the final visit (section 4.4.2.6.) and the laboratory or cabinet findings or adverse events, if detected, have been explained and closed by the investigator.

For the wash-out period - drug's elimination - time when the subjects are out of the clinic, general directions will be given to each subject. They include specific information about feeding, restriction of drugs and overall care.

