7.3.4. Deviation to the Statistical Plan

The study statistical plan will correspond to what is specified in the section 7.3 of this protocol with regards to the methods and criteria for the statistical tests thus established to compare the bioavailability of the study drug.

All deviations should be justified by statistical or scientific evidence and any change should be reported in the original statistical plan, in the study master file and in the statistical pharmacokinetic report and study final report.

Subject data will not be replaced and any missing data will be considered as non-existent data. Likewise, data cannot be removed from the statistical analysis, except for the following cases:

- ⊕ Elimination of date due to vomiting and diarrhea.

Data from the research subjects who suffer from vomiting and diarrhea during the bioequivalence study for immediate release products can be removed from the statistical analysis if vomiting or diarrhea occurs before twice the median for t_{max} or twice the value for t_{max} from the research subject in a given period.

- ⊕ Research subject with very low serum concentrations for the study drugs.

As established by the NOM-177-SSA1-2013, also the research subjects who do not provide evaluable data in a crossed design, both for the test drug and for the reference drug, or who do not provide evaluable data in the single period of a parallel design, should not be included in the statistical analysis.

A research subject is considered to have very low concentrations, if the $AUC_{(a)}$ is $< 5\%$ for the geometric mean for the AUC of the reference drug (it should be calculated without including outliers). Exclusion of data for this reason, will only be accepted under scientific rationale and previous review of the case by the COFEPRIS.

- ⊕ Finally, all data which do not show significant outliers will be considered according to the criteria for outliers in the section 7.3.3 of this protocol. Outliers exclusion should be supported by scientific evidence.

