RATIONALE FOR THE SAMPLE SIZE	The sample size determination was based on the variability seen in the most recent study conducted by the study Sponsor EMR200125-001 (comparative study of the levothyroxine formulations for approval in Europe) where the intrasubject variability for AUC_{0-72h} was 23.7 % and the C_{max} was 17.7 %. Using the most variable parameter AUC_{0-72h} , a difference of 5 %, a power of 90 % and applying the accepted bioequivalence range of 80 % to 125 %, a sample size of 34 subjects was obtained. If a drop rate of 20 % is considered, the sample size should be of 44 subjects.
DOSAGE FORM	Tablets 200 µg.
DOSE	600 µg (3 tablets of 200 µg), orally, with a 10-h fasting state.
PRE-TREATMENT	Not required.
WASH-OUT TIME	35 days.
CLINICAL LABORATORY TESTS	Complete blood count; 4-panel chemistry; urinalysis; liver function tests; HIV, hepatitis B and C, and VDRL test; and qualitative urine test for illicit drugs, and pregnancy test for women. Thyroid profile.
REFERENCE PRODUCT	Eutirox® from Merck, S. A. de C. V. (approved formulation).
TEST DRUG	Eutirox® from Merck, S.A. de C.V. (new formulation)
ENDPOINTS	48.00-h follow-up to collect 26 blood samples to determine levothyroxine (T4) in serum and to calculate the AUC_{0-t} and C_{max} corrected values.
SAMPLING TIMES	-0.50, -0.25, 0.00 pre-dose and at 0.5, 1.0, 1.5, 2.0, 2.5, 3.0, 3.25, 3.5, 3.75, 4.0, 4.25, 4.5, 4.75, 5.0, 5.5, 6.0, 6.5, 8.0, 10.0, 12.0, 24.0 36.0 and 48.0 h post-dose.
SPECIAL REMARKS	Pre-dose sampling will be carried out. Statistical analysis to prove interchangeability will only be made using the corrected values for the parameters C_{max} and AUC_{0-t} . Equivalence margins will be considered as 80 % - 125 %.

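### Could a lost 48-h sample put unequal AUC windows into the primary comparison?

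*Protocol*

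**What the plan says.** Section 7.2 of the protocol defines the primary extent measure, the baseline-adjusted AUC0-t, as running "from time 0 until the last sampling, by means of the trapezoidal rule in pre dose corrected data". The abbreviation list words it almost the same way: "Area under the curve of serum concentration from time 0 until the last sampling time in pre dose corrected data". Neither entry names an hour.

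The intended hour appears elsewhere. Section 1.3 reports from the agency guidance that "bioequivalence studies for this drug should be truncated up to 48 hours". The endpoint row of the summary (12.3) reads "48.00-h follow-up to collect 26 blood samples to determine levothyroxine (T4) in serum" and ties this to calculating the corrected AUC0-t. The schedules in 4.4.3, 4.5.2, 4.5.7 and 12.2 all have 48 h as the last of 26 samples.

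For evaluability, section 7.3.1 requires that a subject "has completed both periods of the study and has at least 60% of their samples with measurable concentrations", and adds a general clause against any uncontrolled circumstance that could alter the result. Section 4.5.5 gives the length of the first period as "from the 16.00 hours prior to the first dose and at least 48.00 hours post-dose", and the second period likewise.

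Section 7.3.4 states "Subject data will not be replaced and any missing data will be considered as non-existent data" and restricts removal of data to listed cases. Among these it says that subjects "who do not provide evaluable data in a crossed design, both for the test drug and for the reference drug" are not to be included. The opening of section 7 places the pharmacokinetic and statistical analysis under the unit's standard operating procedures and NOM-177-SSA1-2013.

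**The concern.** The analysis is a within-subject comparison of log AUC, so a subject's two AUCs should cover the same interval. The 60% rule counts samples without regard to where the gaps lie. A period without its 48-h value still has 25 of 26 samples (96%), and one without 36 h and 48 h has 24 of 26 (92%). Section 4.5.7.1.3 foresees that samples may be rejected, and the two last samples are ambulatory.

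A literal reader could therefore stop the AUC at 36 h in one period and at 48 h in the other. Two identical products would then give that subject a ratio well away from 1. The estimated ratio would shift and the residual variance would grow. If such losses fell mainly on one product, the error rate of the equivalence test would be affected.

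**Working it through.** **Inputs.** From section 7.1: intra-subject CV 23.7% for AUC, difference 5%, power 90%, margins 80% to 125%, 34 subjects, 44 after a 20% drop rate. From 1.2.2.4: T4 half-life 6.2 days, or 148.8 h. From 4.4.3: the sampling times. Assumed, because the protocol gives no baseline-adjusted profile: a one-compartment shape with absorption rate 0.5 to 2 per h, half-life from 148.8 h down to 24 h, and the share of samples lost.

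**The plan's own figure.** σ² = ln(1 + 0.237²) = 0.0546, so σ = 0.2338. The distance to the margin at a ratio of 0.95 is ln 0.95 − ln 0.80 = 0.1719. The requirement per sequence is n ≥ (t(0.95, 2n−2) + t(0.90, 2n−2))² σ² / 0.1719². At n = 17 the right side is (1.694 + 1.309)² × 0.0546 / 0.0295 = 16.7, which is met. At n = 16 it is also about 16.7, which is not met. The total is 34, as stated. 34/0.8 = 42.5, so 43, or 44 for balanced sequences. Exact power is 0.906 at 34 and about 0.96 at 44.

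**How much AUC the last samples carry.** The linear trapezoid on the protocol's times, with C = exp(−kt) − exp(−ka·t), gives:

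| Half-life | AUC0-36/AUC0-48 | AUC0-24/AUC0-48 |
|---|---|---|
| 148.8 h | 0.76 to 0.77 | 0.51 to 0.52 |
| 24 h | 0.85 to 0.86 | 0.64 to 0.66 |

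**One subject with a 36-h window in one period (factor 0.77, n = 34).** The shift in the mean log ratio is ln 0.77 / 34 = −0.0077 if the test period is short, and +0.0077 if the reference period is. The standard error is 0.2338 × √(2/34) = 0.0567. The estimated variance of a within-subject difference, 2σ² = 0.1093, rises by about 0.2614² × (16/17) / 32 = 0.0020. The estimated standard error is then 0.0572.

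- No loss: (0.1719 − 1.694 × 0.0567) / 0.0567 = 1.337, power about 0.909 (exact 0.906).
- Test side short: (0.1642 − 1.694 × 0.0572) / 0.0567 = 1.19, power about 0.88 (simulated 0.878).
- Reference side short: (0.1795 − 1.694 × 0.0572) / 0.0567 = 1.46, power about 0.93 (simulated 0.923).

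Averaged over which product is hit, the simulated value is 0.901.

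**Random losses of the 48-h value only (factor 0.77, 100,000 simulated trials).**

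| Share of subject-periods | Power, n = 34 | Power, n = 44 |
|---|---|---|
| 0% | 0.906 | 0.959 |
| 1% | 0.902 | 0.959 |
| 2% | 0.900 | 0.957 |
| 5% | 0.892 | 0.950 |

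Type I error at ratios of 0.80 and 1.25 was 0.0495 to 0.0516 with 2% or 5% of subject-periods affected, unrelated to product.

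**The alternative of omitting the subject's AUC.** Exact power is 0.906 at 34 and 0.889 at 32, so one subject fewer lies between these. Neither way of handling an isolated loss changes the outlook, and enrolment of 44 leaves 44 − 34 = 10 subjects in hand.

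**Which clauses reach the case.** A subject who misses the 48-h visit has not completed a period that runs to at least 48 h, so 7.3.1 excludes that subject on its natural reading. If a sample was drawn and later rejected, the last sampling still took place at 48 h. The AUC that 7.2 asks for is then unavailable, not redefined to 36 h. The both-products clause of 7.3.4 gives the analyst a ground to leave that subject out of the AUC comparison.

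**The case for a change.** The strongest contrary case is that none of these clauses says so outright. The both-products clause stands under a bullet on very low concentrations. The general clause in 7.3.1 has to be invoked case by case. Section 7.3.4 makes section 7.3 the statistical plan, so the matter is not plainly deferred to another document. All of this stands as a remark on completeness. However, 7.3.4 speaks there of methods and criteria for the tests, while AUC calculation is in 7.2 and falls under the procedures named at the head of section 7.

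Larger effects can also be constructed. With one subject cut at 24 h (factor 0.52) on the test side, power at 34 is 0.815; on the reference side it is 0.938, for a mean of 0.876. If both late samples were lost in 5% of subject-periods, power would be 0.804. If 5% of reference periods alone lost the 48-h value, type I error at a true ratio of 0.80 would be 0.078. The arithmetic holds, but the premises have no support in the protocol. It gives no reason to expect a 5% double loss. Three cryotubes per sample (4.5.7.1.1) make total loss less likely, and the blinded Analytical Unit (4.4.9) leaves no evident route to losses tied to one product.

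It might further be said that the choice would be made with the results in view. Section 4.5.7.1.3 places rejection at receipt and inspection, before storage and assay. A later assay failure is conceivable, but the protocol does not show that the choice would follow knowledge of the concentrations.

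**Conclusion.** No change to the plan is needed. The wording leaves a small gap, since the hour is not written into the AUC definition and a single unusable 48-h value is not named. But no rule prescribes unequal windows. The schedules, section 1.3 and the summary all fix 48 h, and the existing clauses let an analyst treat the case sensibly.

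Even under the unfavourable reading, isolated losses in 1% to 2% of subject-periods move power from 0.906 to between 0.902 and 0.900 at 34 subjects, and by at most 0.002 at 44. Type I error stays at about 0.05. The sample size and the Cmax comparison are untouched.

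A rule computing both periods to the last common time would be one convention among several. It would bring a shorter AUC into an analysis that section 1.3 sets at 48 h, with no clear gain over omitting that subject's AUC. These conclusions rest on the assumed profile shape, on losses being few and unrelated to product, and on the planning CV applying to AUC0-48h. Only the protocol was available for this check.
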